9. SAMPLE SIZE CALCULATIONS AND STATISTICAL PLAN

9.1. Sample Size and Power Calculations

The study is explorative. Not enough preliminary data exists to support accurate calculation of the sample size. However we conducted a sample size analysis based on hypothetical scenarios and knowledge of similar studies. Based on previous studies performed at the Hope Clinic and the Vaccine Research Trials Center, the rate of subjects that become ineligible during the study (i.e. do not meet exclusion/inclusion criteria anymore, lost to follow-ups, unable to have blood draws) is between 5 to 10%. Assuming 10% attrition rate, 88 subjects will be recruited and 1:1 randomized into the two treatment groups, resulting in an expected 80 subjects for data analysis. The sample size is on-par with similar studies. In the case that the sample size of subjects missing any of the 4 draws required for the primary endpoint [meaning draws at days 1, 3, 7(\pm 1), and 30 (\pm 7)] is higher than 10% of the 88 subjects to be recruited for the study, we will recruit extra patients to maintain the target sample size of 80 subjects.

The randomization process will be detailed in the MOP. At the center of this study is the identification of generic innate signatures and finding their correlations with the adaptive immune response. The generic innate signatures will be identified from both traditional immune parameters measured by FACS/Luminex assays and array-based gene expression will be measured by microarray experiments. The generic innate signatures will be identified for different treatment groups separately. The traditional immune parameters and array-based gene expression that change after immunization are considered generic innate signatures. The traditional immune parameters and array-based gene expression that change after immunization are considered generic innate signatures. The traditional immune parameters and array-based gene expression that are correlated with the adaptive immune responses (day 30 OPA titers, day 30 IgG levels, day 180 serotype specific avidity indexes, plasmablasts also) are considered correlation signatures of the innate immune responses.

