Both for sample size consideration and data analysis, we will use different stringency levels for the traditional immune parameters and microarray data, because the traditional immune parameters are measured with less noise, and a traditional immune parameter is more likely than an average gene to be associated with the immune response.

Primary Endpoint 1.

The innate signatures will be detected in each treatment group separately. A two-sided paired paired t-test will be used to test each immune parameter, in order to find immune parameters that change significantly over the baseline. As multiple immune parameters are studied, we use the alpha level of 0.01 to offset multiple testing. With 30 samples in each treatment group in the elderly, we can reject the null hypothesis of equal means with 80% power if the true effect size (mean difference/sigma) is 0.66, using a two-sided paired t-test and the alpha level of 0.01.

For the gene expression, again the innate signatures will be detected in each treatment group separately. The actual data analysis will be performed using the method Significance Analysis of Microarrays (SAM) with paired design. For sample size consideration, we will consider the simpler case of a paired t-test. As the number of genes tested is in the order of tens of thousands, we use the alpha level of 0.0005 to offset the effect of multiple testing. This means an average of one false positive for every 2000 null genes tested, which is an acceptable level as we expect >100 truly differentially expressed genes. In actual data analysis false discovery rate (FDR) will be used. With 30 samples in each elderly treatment group, we can reject the null hypothesis of equal means with 80% power if the true effect size (mean difference/sigma) is 0.88, using a two-sided paired t-test and the alpha level of 0.0005.

Primary Endpoint 3, Secondary Endpoints 2&4.

The correlation signatures will be identified for each treatment group separately. The innate signature markers/genes identified in the analysis of Primary Endpoint 1 will be used in this step for the identification of correlation signature. For the traditional immune parameters, with 30 samples in each elderly treatment group, at the alpha level of 0.01, we can reject the null hypothesis of zero correlation with 80% power if the true correlation is 0.57 using a two-sided test for Pearson's correlation coefficient.

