For the gene expression data, the actual data analysis will be performed using SAM with quantitative outcome. For sample size consideration, we will consider the simpler case of testing the significance of Pearson's correlation coefficient. We use the alpha level of 0.005 to offset the effect of multiple testing. This means an average of one false positive for every 200 null genes tested, which is an acceptable level as we expect the number of innate signature genes under study will be in the hundreds. The alpha level used here is different from that in

Primary Aim 1, because the numbers of multiple tests being conducted are different (several hundreds v.s. tens of thousands in Aim 1). With 30 samples in each elderly treatment group, at the alpha level of 0.005, we can reject the null hypothesis of zero correlation with adaptive immune responses with 80% power if the true correlation is 0.60 using a two-sided test for Pearson's correlation coefficient.

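### The 80% power stated for Primary Endpoint 3 is conditional on a marker first passing Primary Endpoint 1; over both steps it is about 62% at the plan's own detectable effects (one marker, one day)

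*Combined protocol and SAP*

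**What the plan says.** Section 9.1 sizes two steps separately, each within one elderly vaccine group: "With 30 samples in each treatment group in the elderly".

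- **Primary Endpoint 1 (change from baseline).** For immune parameters, 80% power is claimed when the "effect size (mean difference/sigma) is 0.66, using a two-sided paired t-test and the alpha level of 0.01". For genes, it is claimed when the "effect size (mean difference/sigma) is 0.88, using a two-sided paired t-test and the alpha level of 0.0005".
- **Primary Endpoint 3 (correlation with day 30 OPA titers).** For immune parameters at alpha 0.01, the plan says it can reject the "hypothesis of zero correlation with 80% power if the true correlation is 0.57". For genes at alpha 0.005, it can reject the "hypothesis of zero correlation with adaptive immune responses with 80% power if the true correlation is 0.60".

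The steps are linked. Under Primary Endpoint 3, section 9.1 states: "The innate signature markers/genes identified in the analysis of Primary Endpoint 1 will be used in this step for the identification of correlation signature". Section 9.2.1 repeats this rule in the analysis of Primary Endpoint 3. Under exploratory endpoint 4 it adds that, in every group, the correlation signature is contained in the innate signature.

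Section 9.1 also uses the link to set alpha. The gene threshold is relaxed from 0.0005 to 0.005 because several hundred genes are expected in the second step, against tens of thousands in the first. No power over the two steps together is given.

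**The concern.** A marker that misses the first step cannot enter the correlation signature, however strongly it tracks the OPA titer. Reaching the correlation test is itself only about an 80% event at the effect for which the first step was sized. The Primary Endpoint 3 figure takes the multiplicity benefit of the filter, through the looser gene alpha, but deducts nothing for true markers that the filter removes.

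Correlation with the adaptive response is the primary objective (section 2.1). A reader who takes 80% as the sensitivity of the whole procedure would give too much weight to a marker's absence from the list. The markers most exposed are those that correlate well but change only modestly on average.

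**Working it through.** **Inputs, all from section 9.1.** Elderly subjects: 66 / 2 = 33 per vaccine group; less 10% attrition, 33 × 0.9 = 29.7, so n = 30. Step 1: d = 0.66 at two-sided alpha 0.01 (parameters); d = 0.88 at 0.0005 (genes). Step 2: rho = 0.57 at 0.01 (parameters); rho = 0.60 at 0.005 (genes).

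**The plan's own figures.** Step 1 is a paired t-test with 29 degrees of freedom and noncentrality d√n.

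- Parameters: 0.66 × √30 = 3.615 against a critical value of 2.756; power 79.7%.
- Genes: 0.88 × √30 = 4.820 against 3.918; power 79.8%.

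Step 2, by Fisher's z, has power Φ(atanh(rho) × √(n − 3) − z), where z is the two-sided normal critical value.

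- Parameters: 0.6475 × √27 = 3.365; 3.365 − 2.576 = 0.789; power 78.5%.
- Genes: 0.6931 × √27 = 3.602; 3.602 − 2.807 = 0.795; power 78.7%.

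With the bias correction and a t-based critical correlation, these become 79.2% and 79.0%. Simulation gives 79.4% and 79.3%. All four stated figures reproduce within 2 points of 80%.

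**Both steps together.** The nominal product is 0.80 × 0.80 = 64%. With the recomputed powers it is 0.7968 × 0.7917 = 63.1% (parameters) and 0.7977 × 0.7905 = 63.1% (genes). Running both tests on the same 30 simulated subjects (400,000 replicates, bivariate normal, change score correlated with outcome) gives **62.3%** and **61.8%**. If the correlation uses the post-vaccination level instead of the change, with an assumed baseline-to-post correlation of 0.5, the figures are 63.1% and 62.9%.

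**Sensitivity to the first-step effect**, with rho held at the plan's value:

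| Marker type | d | Step 1 | Both steps, simulated | Both steps, product |
|---|---|---|---|---|
| Parameter (rho 0.57) | 0.50 | 50% | 38% | 40% |
| | 0.66 | 80% | 62% | 63% |
| | 0.80 | 94% | 74% | 74% |
| | 1.00 | 99% | 79% | 79% |
| Gene (rho 0.60) | 0.70 | 48% | 36% | 38% |
| | 0.88 | 80% | 62% | 63% |
| | 1.00 | 92% | 72% | 73% |
| | 1.20 | 99% | 79% | 78% |

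**Fold-change rule.** Section 9.2.1 tentatively also requires an average fold change of at least 3 for immune parameters. Its effect depends on the SD of the change, which the documents do not give. Assuming log-normal changes at d = 0.66, the two-step figure is about 0% at a log2 SD of 1.0, 15% at 1.25, 48% at 1.5 and 62% at 2.0.

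**The case against.** The strongest reply is that section 9.1 contains no arithmetic error. Each 80% is a correct detectable effect for a single test, and the restriction to selected markers stands directly before the power statement. The explanation of the gene alpha makes clear that the second step concerns an already reduced set. All of this stands. A reader might infer that the 80% is miscalculated; it is not. What is missing is a statement that it is conditional, together with the figure for the complete path.

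A second reply is that 62% belongs to a marker lying exactly at both minimum effects, and nothing in the plan says such a marker is expected. This also stands, which is why the range matters: for large first-step effects the loss almost vanishes.

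Third, 62% is not the power of the analysis as it will be run. Signatures are sought on three days, and genes are selected by SAM with FDR at most 0.1; section 9.1 itself calls its tests a simplification. If the same effects are assumed on all three days, with between-day correlation of 0.5 to 0.9, the chance of passing both steps on the same day at least once is about 76% to 89%. If the effect appears on one day only, it stays at 62%. Reading 62% as the study's actual power therefore goes beyond the documents. The stated 80% rests on the same one-day, simplified basis, so comparing the two is fair.

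Finally, the study is described as explorative, and nothing in the plan treats absence from the list as evidence against a marker. That limits the consequence. It does not make the 80% a description of the two-step procedure.

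**Conclusion.** The point holds as a correction of what the stated power means. The 80% for Primary Endpoint 3 is valid only for a marker that has already been selected in Primary Endpoint 1. At the plan's own detectable effects, the chance of passing both steps is about 62%, some 18 points lower.

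This assumes n = 30, normal data, a single marker on a single day, and the plan's simplified fixed-alpha tests. The figure approaches 80% only when the first-step effect is about 1.0 SD or more (parameters) or 1.2 SD or more (genes).

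It would go too far to say that the fold-change rule must lower the figure for parameters. It cannot raise it, but under the assumed SDs the result lies anywhere from about 0% to 62%, and the rule is only tentative.

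**What to change.** In section 9.1, label both Primary Endpoint 3 figures and add the two-step figure, for example: *80% conditional on selection in Primary Endpoint 1; about 62% over both steps at the stated effects (single day, simplified tests), approaching 80% only when the first-step effect is about 1.0 SD (parameters) or 1.2 SD (genes) or more.* Add one sentence saying that the tentative fold-change criterion is not in this calculation and can only lower the figure for immune parameters, by an amount that depends on the SD of the change.

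Optionally, report the correlations of all measured FACS/Luminex parameters with day 30 OPA titers without the first-step filter, as a labelled sensitivity table.

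The cost is a few lines of text and a less favourable number in print. The optional table adds more tests and one more output. Sample size, visits, assays and the primary method are unchanged.

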9.2. Data Analysis

9.2.1. General considerations

The young treatment groups are of limited size. The main purpose of the young treatment groups is to provide some indication whether the elderly respond to the vaccines differently than the young. By themselves, the young groups do not have sufficient statistical power to generate reliable innate and correlation signatures. However when used in comparison against elderly groups, and by only considering biological pathways (collections of genes contributing to the same biological process) that are affected by the vaccine, they can provide some indication as to how different the response is in the elderly compared to the young. Thus for data analysis, the young treatment groups will be used only in exploratory endpoints. The primary and secondary endpoints will focus on the elderly groups.

The analyses will be based on population with critical time points met, defined as those who received vaccine per label and got the 4 draws required for the primary endpoint, i.e. draws at days 1, 3, 7 (\pm 1), and 30 (\pm 7) within the required windows. Data from the study will be analyzed using the statistical software R³¹. High-throughput data will be analyzed using appropriate methods, either by stand-alone software or modules in leading statistical softwares, e.g. the Bioconductor in the R framework³². For cytokine data, missing values will be dealt with using multiple imputations. For microarray data, nearest neighbor method and local least squares may be used to fill missing values. Unsupervised learning techniques such as PCA, PLSDA, clustering, and factor analysis ³³ will be used for the visualization and identification of global patterns. For descriptive endpoint (primary endpoint 2), we will generate summary statistics, and visualize the data using histograms and boxplots when applicable. For the identification of innate signatures, the two treatment groups will be analyzed separately.

Analyses of primary endpoints:

1. Identification of generic innate immune signatures [Traditional immune parameters measurements + array-based gene expression] at days 1, 3 and 7 post vaccination with either PPV23 or PCV13 in the elderly.

The innate signatures will be detected in each elderly treatment group separately. We will take the measurements on the day of vaccination as baseline. For traditional immune parameters, we will test if an immune parameter shows significant change over baseline at day 1, 3, and 7 after each vaccination, using a two-sided paired t-test. In addition, for each immune parameter, the fold-change over baseline will be calculated for every subject. The average (arithmetic mean) fold change over the 30 subjects will be combined with the test p-value in a selection criterion as appropriate. Based on previous studies similar in nature, the tentative selection criterion is pvalue ≤ 0.01 and average fold change ≥ 3 .

For the gene expression data, again the innate signatures will be detected in each elderly treatment group separately. We will use the method Significance Analysis of Microarrays (SAM) ³⁴ with paired design to find differentially expressed genes over the baseline. False discovery rate (FDR) will be used as selection criterion. The tentative selection criterion is FDR \leq 0.1.

2. Measurement of adaptive immune responses [Opsonophagocytosis assay (OPA) titers] at day 30 post vaccination with either PPV23 or PCV13 in the elderly.

The OPA titers will be presented as descriptions of the actual values separately in both study elderly populations (PPV23 and PCV13 recipients). Summary statistics, boxplots and histograms will be used to summarize the data.

3. Correlation of signatures of generic innate immune responses at days 1, 3 and 7 that correlate to adaptive immune responses [Opsonophagocytosis assay OPA titers] at day 30 post vaccination with either PPV23 or PCV13 in the elderly.

The correlation signatures will be detected in each elderly treatment group separately. The innate signature markers/genes identified in Primary Endpoint 1 will be used in this step for the identification of correlation signature.

For traditional immune parameters, we will calculate the correlation coefficient between the immune parameter and the adaptive immune response (day 30 OPA titers). The p-values associated with the correlation coefficients will be used to select traditional immune parameters

that are associated with the respective adaptive immune responses (day 30 OPA titers). The tentative selection criterion is p-value ≤ 0.01 .

For gene expression data, we will use the method Significance Analysis of Microarrays (SAM) with quantitative outcome to identify genes that are significantly associated with the respective adaptive immune responses (day 30 OPA titers). False discovery rate (FDR) will be used as selection criterion. The tentative selection criterion is FDR ≤ 0.1 .

Analyses of secondary endpoints:

1. Comparison of the serotype specific IgG levels at day 30 post vaccination with either PPV23 or PCV13 in the elderly.

Descriptive analysis, boxpots and histograms, will be conducted to present the data. Testing between the two elderly treatment groups will be conducted using unpaired t-test after proper data transformation. In the case that near-normality cannot be achieved with data transformation, we will resort to the Wilcoxon test.

2. Correlation of signatures of generic innate immune responses at days 1, 3 and 7 with serotype specific IgG levels at day 30 post vaccination with either PPV23 or PCV13 in the elderly.

The analysis will be conducted in each elderly treatment group separately. For traditional immune parameters, we will calculate the correlation coefficient between the immune parameter and the adaptive immune response (IgG levels at day 30 post vaccination). The p-values associated with the correlation coefficients will be used to select traditional immune parameters that are associated with the respective adaptive immune responses (IgG levels at day 30 post vaccination). The tentative selection criterion is p-value ≤ 0.01 .

For gene expression data, we will use the method Significance Analysis of Microarrays (SAM) with quantitative outcome to identify genes that are significantly associated with the respective adaptive immune responses (IgG levels at day 30 post vaccination). False discovery rate (FDR) will be used as selection criterion. The tentative selection criterion is $FDR \le 0.1$.

3. Comparison of the serotype-specific avidity indexes in a subset of up to 6 vaccinees per vaccine group at day 180 post vaccination with either PPV23 or PCV13 in the elderly.

Descriptive analysis, boxpots and histograms, will be conducted to present the data. Testing between the two elderly treatment groups will be conducted using unpaired t-test after proper data transformation. In the case that near-normality cannot be achieved with data transformation, we will resort to the Wilcoxon test.

CONFIDENTIAL

4. Correlation of signatures of generic innate immune responses at days 1, 3 and 7 with serotype specific avidity indexes in a subset of up to 6 vaccinees per vaccine group at day 180 post vaccination with either PPV23 or PCV13 in the elderly.

The analysis will be conducted in each elderly treatment group separately. For traditional immune parameters, we will calculate the correlation coefficient between the immune parameter and the adaptive immune response (serotype specific avidity indexes at day 180 p) the p-values associated with the correlation coefficients will be used to select traditional immune parameters that are associated with the respective adaptive immune responses (serotype specific avidity indexes at day 180). The tentative selection criterion is p-value ≤ 0.01 .

For gene expression data, we will use the method Significance Analysis of Microarrays (SAM) with quantitative outcome to identify genes that are significantly associated with the respective adaptive immune responses (serotype specific avidity indexes at day 180). False discovery rate (FDR) will be used as selection criterion. The tentative selection criterion is $FDR \le 0.1$.

5. Comparison of the adaptive immune responses [Opsonophagocytosis assay (OPA) titers] at day 30 post vaccination with either PPV23 or PCV13 in the elderly.

Descriptive analysis, boxpots and histograms, will be conducted to present and visually contrast the data. Testing between the two elderly treatment groups will be conducted using unpaired t-test after proper data transformation. In the case that near-normality cannot be achieved with data transformation, we will resort to the Wilcoxon test.

Analyses of exploratory endpoints

1. Correlation of signatures of generic innate immune responses at days 1, 3 and 7 with adaptive immune responses [Opsonophagocytosis assay OPA titers specifically] at day 30 post vaccination among subjects in different age strata

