For all endpoints, our data analysis will be based on all subjects who are randomized, receive vaccination per label, and for whom there is a blood sample taken at the 2 required time points (Day 0 and Day 30 + 7 - 7 days) and or Day 0 and Day 180.

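### Sections 9.2.1 and 9.2.2 define two different analysis populations with no order of precedence; the stricter one drops valid day-30 OPA and IgG data for early draws those endpoints never use

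*Combined protocol and SAP*

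**What the plan says.** Two paragraphs of the combined protocol and SAP each define who is analysed.

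- Section 9.2.1 (General considerations) limits the analyses to "those who received vaccine per label and got the 4 draws required for the primary endpoint", and lists days 1, 3, 7 (±1) and 30 (±7), all within window. It does not restrict this to particular endpoints.
- Section 9.2.2 (Patient populations) says: "For all endpoints, our data analysis will be based on all subjects who are randomized, receive vaccination per label". Beyond that it asks for only two samples: day 0 and day 30 (±7), and/or day 0 and day 180. No day 1, 3 or 7 draw is required.

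Neither section cites the other, and neither set is labelled primary, sensitivity or endpoint-specific.

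Other text points both ways. Section 9.1 counts "subjects missing any of the 4 draws required for the primary endpoint" against the target: if they exceed 10% of the 88, "we will recruit extra patients to maintain the target sample size of 80 subjects". That fits 9.2.1. The note in section 4.3 lets the same subjects continue, at the investigator's discretion, with draws for secondary and exploratory endpoints. That has little purpose if 9.2.1 then excludes them.

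**The concern.** Primary 2 (description of day-30 OPA), Secondary 1 (day-30 IgG by arm) and Secondary 5 (day-30 OPA by arm) use no day 1, 3 or 7 sample. Under 9.2.1, a randomised and vaccinated subject with a valid day-30 sample still drops out of all three after missing one early draw, or after coming a day late for day 1 or day 3, for which section 7.6 gives no window. Secondary 1 and 5 are the only between-arm tests at day 30 among the primary and secondary endpoints. They would then be conditioned on post-randomisation attendance, in a study that section 7.8.3 describes as open.

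Primary 1 also loses usable data. The plan says "we will test if an immune parameter shows significant change over baseline at day 1, 3, and 7 after each vaccination". Missing only day 3 discards valid day-1 and day-7 pairs, and missing only day 30 discards all three days although Primary 1 uses no day-30 sample.

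Section 9.4 requires an amendment for changes to principal features. Because both rules are already in the protocol, either could be adopted after the data are seen without one.

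**Working it through.** **1. Do the two rules differ?** Day-0 blood is taken at the baseline visit (section 7.3), so in practice the 9.2.1 set lies inside the 9.2.2 set.

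| Draws obtained | 9.2.1 | 9.2.2 |
|---|---|---|
| 0, 1, 3, 7, 30 in window | in | in |
| 0, 1, 7, 30 (day 3 missed) | out | in |
| 0 and 180 only | out | in |

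Neither rule fits every endpoint. 9.2.1 is too strict for the day-30 endpoints. 9.2.2 read literally admits to Primary 1 subjects with no early sample, for whom it cannot be computed. The imputation text in 9.2.1 covers missing cytokine and microarray values; it does not say whether a subject missing a whole draw is admitted.

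**2. The plan's own figures.** Section 9.1 works "With 30 samples in each treatment group in the elderly". Paired t-test power = P(T′ > t(1−α/2, n−1)), where T′ is noncentral t with n−1 df and noncentrality d√n. At n = 30 and 80% power this gives d = 0.662 for alpha 0.01 (plan: 0.66) and 0.882 for alpha 0.0005 (plan: 0.88). Both reproduce. At 33 and 28 subjects the values are 0.63 and 0.69 (alpha 0.01), and 0.83 and 0.92 (alpha 0.0005).

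**3. Day-30 comparison between arms.** 66 elderly / 2 = 33 per arm. The test is the unpaired t-test, with 2n−2 df and noncentrality d√(n/2). The plan states no alpha for Secondary 1 and 5, so both levels are assumptions. No replacement is assumed.

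| n per arm | Excluded of 33 | Detectable d, alpha 0.05 | Power at d = 0.70, alpha 0.05 | Detectable d, alpha 0.01 |
|---|---|---|---|---|
| 33 | 0 | 0.70 | 80% | 0.86 |
| 30 | 3 (9%) | 0.74 | 76% | 0.91 |
| 28 | 5 (15%) | 0.76 | 73% | 0.94 |
| 26 | 7 (21%) | 0.79 | 70% | 0.98 |

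**4. How many valid day-30 samples are lost?** Assume each of days 1, 3 and 7 is independently missed or out of window with probability p. The excluded share among those with a day-30 sample is 1 − (1−p)³.

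| p | Share | Of 33 per arm |
|---|---|---|
| 1% | 2.97% | 1.0 |
| 2% | 5.88% | 1.9 |
| 3% | 8.73% | 2.9 |
| 5% | 14.26% | 4.7 |

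**5. The two rules at one miss rate.** Let each of the four draws be missed with probability 2.6%, so that 1 − 0.974⁴ ≈ 10% miss at least one. Of 66 elderly, 66 × 0.974 = 64.3 have a day-30 sample and 66 × 0.974⁴ = 59.4 have all four. That is about 32 against 30 per arm, or 0.71 against 0.74 SD at alpha 0.05.

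**6. Possible shift in an arm's mean.** If k of 33 are excluded and differ from those retained by δ SD (assumed), the retained mean differs from the full mean by kδ/33. For k = 1 and δ = 0.5 this is 0.02 SD; for k = 3 and δ = 1.0, 0.09 SD; for k = 4.7 and δ = 1.0, 4.7/33 = 0.14 SD. If both arms are affected alike, most of this cancels in the comparison.

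**The case against.** **The data loss is conditional.** It occurs only if 9.2.1 governs. Section 9.2.2 carries the population heading and claims every endpoint, and under it no day-30 value is lost for a missed early draw. This stands. What is established without condition is the contradiction.

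**33 per arm is the wrong comparator.** It ignores subjects with no day-30 sample, and the attrition rate in section 9.1 already names those "lost to follow-ups, unable to have blood draws". This is fair. The like-for-like contrast in step 5 is about 0.71 against 0.74 SD. Late visits, however, are not named in that rate.

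**Replacement limits the loss.** Section 9.1 provides for extra recruitment, so the rows at 28 and 26 are largely cases the plan means to correct. That holds for the count, although the commitment is to 80 overall and not per arm. It does not bring the excluded subjects back into the randomised comparison.

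**One complete-draw set is defensible.** Primary 3 takes its markers from Primary 1, and section 9.2.1 averages fold change over 30 subjects, so a common set has a purpose. That is a reason to keep it as a sensitivity set. It gives no reason to apply it to endpoints that use only day 30.

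**The study is exploratory, and section 9.4 allows further ad hoc analyses.** True, and it lowers the stakes. Permission for additional analyses still does not say who belongs in the planned ones. Differential attendance by arm is not shown anywhere in the documents.

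**Conclusion.** The concern holds. The contradiction is plain on the page and depends on no assumption: two unranked rules give different sets, and neither suits all endpoints. The numerical consequence is small: with about 10% missing at least one draw, roughly two to three subjects per arm and 0.03 SD in detectable difference. The sizes rest on assumed miss rates, independent misses, an assumed alpha and no replacement; none is a bound. Bias from conditioning on attendance is possible but not demonstrated. The text should be corrected because the choice of set would otherwise remain open after the data are seen, and the correction costs little.

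**What to change.** Replace both paragraphs with one set per endpoint, all among subjects randomised and vaccinated per label, with draws in the stated windows (k = 1, 3 or 7):

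- Primary 1 at day k: day 0 and day k.
- Primary 2, Secondary 1, Secondary 5: day 30, whatever the attendance at days 1, 3 and 7.
- Primary 3, Secondary 2: day 0, day k and day 30.
- Secondary 3: the day-180 avidity subset. Secondary 4: that subset with day 0 and day k.
- Exploratory endpoints: the draws each one uses.

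Keep the four-draw completers as a named sensitivity set, which holds the subjects constant across Primary 1 to 3, and as the basis for the replacement count in section 9.1. Report N, and the number excluded with reasons, by endpoint and arm.

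The cost is protocol and SAP wording only. N will vary slightly between endpoints and must appear in each table, and Primary 2 and Primary 3 will no longer cover exactly the same subjects in the main analysis; the sensitivity set keeps that alignment.
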